4.4. Run-in period

Patients must not have used any prescription or over-the-counter medication or herbal remedy taken with an intent to improve or treat NASH or liver disease or obesity or diabetes for the 3 months prior to liver biopsy and for the 3 months prior to randomization. AntiNASH agents include: thiazolidinediones, vitamin E, metformin, UDCA, SAM-e, betaine, milk thistle, gemfibrozil, anti-TNF therapies, and probiotics. Antidiabetic agents include but are not limited to: insulin, biguanides, sulfonylureas, metformin and thiazolidinediones. These agents are not to be used during screening nor for the duration of the trial (except in the form of assigned study treatment or treatment for new onset diabetes).

19

Any over-the-counter medication or herbal remedy that is being taken with an intent to improve hyperlipidemia will not be allowed for at least 3 months prior to randomization and will be discouraged after randomization. Patients will be allowed to continue on prescription anti-hyperlipidemic agents. Patients will be interviewed in a detailed fashion at screening, randomization, and at every clinic visit to document the absence of such use. If using a statin or fibrate medication, the patient must have been on a stable dose in the 3 months prior to liver biopsy and must have been on a stable dose in the 3 months prior.

5. Trial protocol

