5.8.1.1. Safety issues related to thiazolidinediones

• Hepatotoxicity: The first generation TZD, troglitazone, was associated with idiosyncratic hepatotoxicity, and very rare cases of liver failure, liver transplantation, and death. Troglitazone has been withdrawn from clinical use. The second-generation thiazolidinediones appear to be significantly less hepatotoxic. A review of risk of hepatotoxicity associated with second-generation TZD agents is provided in section 2.4. We intend to minimize the risk of hepatotoxicity (or its consequences) (a) by closely monitoring the aminotransferase levels during the study period (at 2, 4, 8, 12, 16, 24, 32, 40, 48, 56, 64, 72, 80, 88, 96, and 120 weeks after randomization), (b) by discontinuing study medication in patients with severe hepatotoxicity (defined as ALT or AST greater than 10 times the ULN in the local lab OR absolute AST or ALT greater than 500 U/L OR serum total bilirubin at least 2.5 mg/dL and at least half of it is direct bilirubin), (c) by avoiding the other potential hepatotoxic agents, and (d) by instructing the patients about self-identification of symptoms associated with hepatotoxicity (i.e., yellow eyes, dark urine, unexplained anorexia, asthenia, or right upper quadrant abdominal pain).

Those who exhibit ALT or AST elevation that is not to the extent described above but who develop a 1.5-fold or greater elevation in ALT or AST from their baseline value and

absolute ALT or AST greater than 250 U/L OR total bilirubin at least 1.5 mg/dL and at least half of it is direct bilirubin OR develop symptoms suggestive of acute hepatotoxicity (i.e., jaundice, nausea, vomiting, abdominal pain, fatigue, anorexia, dark urine) will have their liver biochemistries checked on a weekly basis. If ALT, AST, and/or bilirubin levels decline or stabilize, subjects will have their liver biochemistries checked monthly for 3 months and then according to the protocol schedule. If ALT or bilirubin continues to rise on two consecutive measurements following the initial rise in ALT, AST or bilirubin or if the patient develops symptoms of hepatotoxicity, subjects will be considered to have developed significant hepatotoxicity and the study medication will be discontinued indefinitely.

Patients in whom the study medication has been discontinued due to significant hepatotoxicity will be followed according to the protocol and will be offered a liver biopsy at the conclusion of the study.

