5.8.1.2. Safety issues related to placebo

In the Diabetes Prevention Program (DPP), the incidence of diabetes in the placebo group was 11.0 cases per 100 person-years (64). Based on this, it is anticipated that at least 18 subjects in the placebo group will develop new-onset diabetes during their participation in the trial. Participants will be seen frequently during the study period for assessment of symptoms consistent with uncontrolled hyperglycemia and will have fasting glucose levels measured at 24, 48, 72, 96, and 120 weeks after randomization (at 48, 96 and 120 weeks this measurement is part of the OGTT). Patients with a fasting glucose of at least 126 mg/dL will have the test repeated within 6 weeks to confirm the diagnosis of new-onset diabetes. Patients with a diagnosis of new-onset diabetes will be managed according to the following stepped care approach and the primary care physician will be notified.

- (a) Lifestyle counseling to reduce excess body weight and increase exercise
- (b) Education on diabetic diet

- (c) If fasting glucose remains greater than 140 mg/dL after three months or if patient develops symptomatic diabetes, treatment will be initiated. The suggested treatment would begin with metformin or sulfonylurea as the preferred agent.
- (d) If patient still is unable to maintain glycemic control, primary care physician may request unmasking of the study medication and should institute necessary measures for diabetes management. Study medication will not be unmasked to the investigator. These patients will be followed at scheduled intervals to collect other outcome data; however, they will not have the OGTT scheduled for the visits at 48, 96, and 120 weeks but will have only fasting glucose levels measured.

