5.13. Procedures for unmasking treatment assignment

Treatment assignments are double masked throughout the study until all data collection for the PIVENS trial has been completed (i.e., after completion of the 24 week post trial Follow-up for all patients). Every effort will be made to maintain the masking throughout the study except in emergency situations. The code of specific pharmacological treatment will not be broken without the knowledge of the clinical center's principal investigator.

Unmasking of study medication will occur under the following conditions:

- Severe allergic reaction (Stevens-Johnson Syndrome): Study medication is stopped indefinitely. The patient, primary care provider (PCP), and the investigator will be unmasked.
- **Pregnancy during the study**: Study medication will be stopped indefinitely, and the coded medication will be unmasked. The patient, PCP, and investigator will be notified of the assigned treatment and the associated risks of teratogenicity.
- **Development of hepatotoxicity**: Study medication will be discontinued according to the guidelines in section 5.8.1.1. The patient, PCP, and the investigator will be unmasked.
- **New onset diabetes**: The patient will be referred to their PCP and managed according to the stepped care approach defined in section 5.8.1.2. The patient and PCP may be unmasked to the study medication but the investigator will continue to be masked.

In unforeseen situations where the clinical center principal investigator considers unmasking is in the best interest of the participant's health and well being, unmasking may be done after notifying the Executive Committee.

The Data and Safety Monitoring Board will review all instances of unmasking that occur.

6. Statistical design and analysis

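### The new-onset-diabetes exception in section 4.4 leaves out no drug class, so an open-label thiazolidinedione may be given on top of masked pioglitazone, or in the other arms before the week-96 biopsy

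*Protocol*

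**What the plan says.** Section 4.4 lists thiazolidinediones twice, once among the antiNASH agents and once here: "Antidiabetic agents include but are not limited to: insulin, biguanides, sulfonylureas, metformin and thiazolidinediones". The ban covers screening and continues after randomization, "nor for the duration of the trial (except in the form of assigned study treatment or treatment for new onset diabetes"). Exclusion criteria 8 and 9 in section 4.3 also name the class, but only for the three months before biopsy and before randomization.

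Section 5.8.1.2 sets out the stepped care for new-onset diabetes. After lifestyle and dietary steps, drug treatment starts at step (c): "The suggested treatment would begin with metformin or sulfonylurea as the preferred agent". If control still fails, step (d) says the "primary care physician may request unmasking of the study medication and should institute necessary measures for diabetes management". It adds: "Study medication will not be unmasked to the investigator". Section 5.13 repeats the rule: "The patient and PCP may be unmasked to the study medication but the investigator will continue to be masked".

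Section 5.8.1.1 lists, among its hepatotoxicity safeguards, safeguard (c): "by avoiding the other potential hepatotoxic agents".

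**The concern.** The exception is needed, because patients who become diabetic must be treated. But it is written for all the listed agents at once, and one of them is the class of the masked study drug. A primary care physician who has not asked for unmasking could prescribe a thiazolidinedione to a patient already taking pioglitazone 30 mg daily. The investigator, kept masked, could not confirm the duplication. Section 3.3.2 itself describes liver injury, edema and dose-dependent weight gain with this class. It mentions one of 11 NASH patients withdrawn from a pioglitazone study after a 6-fold rise in ALT.

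The same wording lets a placebo or vitamin E patient receive the class under test before the biopsy that decides the primary outcome.

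**Working it through.** **1. Is a thiazolidinedione barred anywhere once diabetes is diagnosed?**
- Section 4.4: barred in general, then exempted as treatment for new-onset diabetes, with no class excepted.
- Section 4.3, criteria 8 and 9: apply only before biopsy and randomization.
- Section 5.8.1.2(c): states a preference for the first agent and prohibits nothing.
- Section 5.8.1.2(d): leaves the choice of treatment to the physician.
- Section 5.8.1.1, safeguard (c): a general aim that names no drug.

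No passage prohibits it.

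**2. Does anything have to happen first?** The four listed triggers in section 5.13 compare as follows.

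| Trigger | Study medication | Unmasking |
|---|---|---|
| Severe allergic reaction | Stopped | Patient, physician, investigator |
| Pregnancy | Stopped | Patient, physician, investigator |
| Hepatotoxicity | "Study medication will be discontinued according to the guidelines in section 5.8.1.1" | Patient, physician, investigator |
| New-onset diabetes | No stop stated | Optional for patient and physician; investigator stays masked |

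Neither a stop nor unmasking is required before another antidiabetic drug is chosen.

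**3. How many cases of diabetes does the protocol expect?** Section 5.8.1.2 takes 11.0 cases per 100 person-years and section 6.5 plans 80 patients per group. Over two years, 80 × 0.11 × 2 = 17.6, which reproduces the stated 18 for placebo. Sections 3.4 and 5.8.1.3 assume the same for vitamin E. No figure is given for pioglitazone.

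**4. Can the number with duplicated treatment be computed?** It would be (cases on pioglitazone) × (share reaching the late step in time) × (share given a thiazolidinedione). The protocol gives none of the three. As pure assumption, take 25% to 100% of 18 cases, half reaching the late step, and 5% to 25% of those given the class:
- low: 18 × 0.25 × 0.5 × 0.05 = 0.11
- high: 18 × 1.00 × 0.5 × 0.25 = 2.25

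The ends differ twentyfold and depend wholly on the assumptions. I do not use them as an estimate.

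**5. When could it happen?** Section 5.8.1.2 measures fasting glucose at weeks 24, 48, 72, 96 and 120, allows up to 6 weeks for the confirmatory repeat, and then waits three months (13 weeks). On that route the first drug comes at:
- 24 + (0 to 6) + 13 = weeks 37 to 43
- 48 + (0 to 6) + 13 = weeks 61 to 67
- 72 + (0 to 6) + 13 = weeks 85 to 91

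These weeks are not fixed. Step (c) also starts treatment when diabetes becomes symptomatic, without the wait, and its choice of first agent is only a suggestion.

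**6. How close is routine liver monitoring then?** By section 5.4, hepatic panels fall at weeks 2, 4, 8, 12 and 16, which is 5 in the 16 weeks after study drug starts. From week 16 they are 8 weeks apart. A drug added at any time from week 40 to week 80 meets 2 scheduled panels in its first 16 weeks, the first up to 8 weeks away.

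**The case against.** The strongest reply is that the permission is read out of silence. Nothing in the protocol recommends a thiazolidinedione for diabetes, the suggested agents are others, and safeguard (c) in 5.8.1.1 would be breached by adding one. It stands that the protocol does not direct this treatment, and a reader who inferred that it did would be wrong. But 4.4 names the class and then exempts its use, and a general aim does not clearly override that.

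Section 3.6 refers to standardized recommendations on medicines and co-morbid illness. These, or the notification to the primary care physician, may carry a warning. Their wording is not in the protocol, so they can be neither credited nor faulted. If they contain a bar, the fix shrinks to a cross-reference.

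Existing safeguards are real. Step (d) offers unmasking in the same sentence that hands over diabetes management. Concomitant drugs are reviewed at most visits, and an investigator who knows that one patient in three is on pioglitazone should be alerted by a listed thiazolidinedione. Section 5.13 lets the principal investigator unmask in unforeseen situations. A reader might infer that nothing acts until serious liver injury. That is not so: 5.8.1.1 starts weekly tests below the stopping thresholds, on a 1.5-fold rise with ALT or AST above 250 U/L, a bilirubin criterion, or symptoms, and section 6.6 gives the DSMB quarterly reports. Still, each of these is optional or reacts once the drug has been started.

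It is also fair that diabetes, unlike the other three triggers, is not a toxicity of an insulin sensitizer. A mandatory stop for diabetes as such would be wrong. The stop is needed only when a thiazolidinedione is to be added.

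**Conclusion.** The gap is in the text, and it is minor. Followed as written, the protocol permits an open-label thiazolidinedione on top of masked pioglitazone, and in the other two arms before the week-96 biopsy. The sequence is unlikely: the patient must develop diabetes, need drug treatment and be prescribed this class, normally after another has failed. For scale, section 3.3.2 reports ALT above three times the upper limit in 0.26% on pioglitazone and 0.25% on placebo in clinical studies.

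Two further readings are not supported. One is a count of affected patients, since its factors are missing from the protocol. The other is a material loss of power or a biased primary comparison: any such effect should be negligible, and none is claimed. Metformin, also listed as an antiNASH agent, is permitted on purpose and is not part of this point.

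**What to change.** In 4.4, in 5.8.1.2(c)–(d) and in the diabetes item of 5.13, add a clause to this effect:

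- The new-onset-diabetes exception does not cover thiazolidinediones until the week-96 biopsy has been done.
- If the treating physician judges one necessary, the study tablet (pioglitazone or its placebo) is stopped before it starts, in every arm alike. The softgel (vitamin E or its placebo) continues.
- The investigator stays masked, and the physician may still be unmasked on request, as now.
- The patient stays in the assigned group and has the week-96 biopsy.

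State the same in the notification to the primary care physician that 5.8.1.2 already requires.

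Stopping the tablet in all arms removes the duplication without disclosing the assignment. Compulsory unmasking of the physician is better avoided: a thiazolidinedione prescribed, or withheld, after unmasking could hint at the assignment to the masked investigator.

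The cost is small. One late-line class becomes conditional, and the few patients who need it lose the study tablet. Metformin, sulfonylureas and insulin stay open, and sample size, data collection and analysis do not change. A placebo or vitamin E patient could still receive a thiazolidinedione where it is judged necessary; that is accepted for the patient's care.

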5.1. Visit schedule overview

The patient-related activities of the PIVENS trial can be divided into 4 phases:

- Screening for eligibility for enrollment (2 visits over a maximum of 24 weeks)
- Randomization to treatment (1 visit)
- Treatment phase (15 visits over 96 weeks)
- Post-treatment washout phase (1 visit at 120 weeks)

The visit and data collection schedule described below in detail is summarized in Appendix 9.3.

5.2. Screening and baseline data collection

Patients who appear to be eligible after chart review and completion of standard of care tests and procedures for NASH will be invited to undergo screening. Recording of screening data on NASH CRN forms may not start until the patient has signed the consent statement. Screening and baseline data collection procedures will include questionnaires, physical examination, measurement of fasting serum glucose, routine liver tests, and urine analysis. Prior therapy for NASH will be reviewed, and patients will be asked to stop any specific antiNASH treatment such as thiazolidinediones, vitamin E, metformin, UDCA, SAM-E, milk thistle, betaine, or gemfibrozil, anti-TNF therapies, or probiotics. Patient charts will be reviewed for historical information and previous liver biopsy findings. Patients who have not had a liver biopsy previously or whose previous liver biopsy does not meet the requirements for this trial will undergo a liver biopsy as part of screening for the trial.

All participants who sign the consent statement will be registered in the trial database. Each participant who starts screening will be accounted for at the end of screening, as either a screening success (enrolling in the trial) or a screening failure. A screening failure is defined as a participant who signed the consent form, but is found to be ineligible prior to randomization; screening failures include patients who meet medical eligibility criteria but who refuse enrollment in the trial. Reason for screening failure will be recorded in the trial database.

Screening and baseline data collection will be conducted over two clinic visits completed on separate calendar days. The goal of the first screening visit is to obtain consent and record data regarding the trial's inclusion and exclusion criteria; the goal of the second screening visit is to complete collection of baseline data on patients who appear eligible. If a liver biopsy is required, it will be done after the patient has been found to be eligible with respect to other inclusion and exclusion criteria. The procedures completed during screening are:

- Screening visit 1: Determination of eligibility will be based mostly on chart review of standard of care tests and procedures that were completed before screening visit 1. The patient will sign the consent at screening visit 1 to obtain any tests and procedures needed to finalize eligibility after chart review and will undergo a history and physical examination to identify other illness and contraindications for participation. Anthropomorphic assessments (body weight [kg], body height [m], body mass index [BMI], waist circumference [cm], hip circumference [cm] and waist-to-hip ratio, triceps skin fold thickness, mid-upper arm circumference); vital signs (systolic and diastolic blood pressure, heart rate, respiratory rate, body temperature); and general physical findings, including hepatosplenomegaly, peripheral manifestations of liver disease, ascites, wasting or fetor, will be collected and recorded. History of prior liver biopsies and use of antiNASH, antidiabetic, statin and fibrate medications in the 3 months prior to the biopsy will be obtained and recorded. Laboratory test results that need to be recorded from chart review or obtained as part of screening visit 1 include: tests for hepatitis B (HBsAg) and hepatitis C, ANA, anti-mitochondrial antibody, ceruloplasmin (if patient is less than 40 years old), A1AT concentration, iron overload and hepatic iron index, fasting serum glucose, CBC, metabolic panel (sodium, potassium, chloride, bicarbonate, calcium, phosphate, BUN, creatinine, uric acid, albumin, total protein), fasting lipid profile (total cholesterol, triglyceride, LDL, HDL). Frequency and amount of alcohol intake will be obtained. Women of childbearing potential must have a negative pregnancy test.
- **Baseline liver biopsy**: Patients who have not had a liver biopsy within 6 months of randomization or whose previous liver biopsy is not available for review or whose previous liver biopsy is of inadequate quality or whose previous biopsy was done within 3 months of using antiNASH medication (eg, thiazolidinediones, vitamin E, metformin, UDCA, SAM-e, betaine, milk thistle, gemfibrozil, anti-TNF therapies, or probiotics) must have a liver biopsy prior to randomization. The biopsy should be done once the patient has been found to be eligible with respect to all other criteria. Biopsy slides must be of adequate size (1.5 cm or more) and of adequate quality for interpretation. The patient must have not been using antiNASH drugs in the 3 months prior to biopsy, and the patient must have histologic evidence of definite or possible NASH as described in section 5.7 of this protocol.

In the case of a biopsy done previously as standard of care, the NASH CRN study physician should check if tissue blocks and/or additional slides can be obtained from the original biopsy. If the liver biopsy is completed as part of screening for this trial, the liver tissue will be prepared for light microscopy and stains will include hematoxylin and eosin, Masson's trichrome and iron stain; additionally, a piece of liver tissue will be snap frozen and stored at -70 degrees C and set aside for banking.

5. Trial protocol

Clinic staff should note that the date of the biopsy establishes a hard window for completion of screening for randomization – randomization must take place within 6 months (183 days) of the date of biopsy. If the biopsy is more than 3 months old when the patient enters screening and if the patient has medications that need to be washed out, the biopsy will be too old by the time randomization occurs. Clinic staff will have to monitor completion of screening procedures and speed things up if the closing date on the 6 months biopsy window is getting close.

Screening visit 2: Patients will provide blood for banking (measurements to be done on banked serum will include vitamin E level). Patients will complete a nutritional questionnaire (Block 98), a health-related quality of life questionnaire (SF-36), life time drinking history questionnaire (Skinner), functional activity questionnaire, and liver symptoms questionnaire. Laboratory tests include: GGT, prothrombin time, HbA1c, hepatic panel (total and direct bilirubin, AST, ALT, alkaline phosphatase), microalbuminuria. A standard 75 g OGTT with fasting serum glucose, insulin, and C-peptide will be administered. Women of childbearing potential must have a negative pregnancy test. Patients will undergo a DEXA scan to estimate total body fat. All patients will be given information on a healthy life style and diet appropriate for their weight and other factors.

The NASH CRN clinic data system will include software to check patient eligibility based on keyed data forms. The eligibility check task may be run at any time, and there is no limit on the number of times it may be run. The output from the task will list the eligibility checks that the patient has failed and a summary finding that the patient is eligible or ineligible for the trial. Thus staff can use this task to identify the items that still need to be completed, keyed, or verified after data from screening visit 1 are keyed and again after data from screening visit 2 are keyed. The randomization visit should not take place until the eligibility check indicates that the patient is eligible except for the items that can be completed only at the randomization visit.

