5.3. Randomization visit

The randomization visit is the visit at which randomization takes place and the patient is issued the study medication randomly assigned to the patient. Randomization is the act of generating the random study medication assignment and is the procedure which defines a patient's enrollment into the trial. Randomization can only occur after eligibility has been fully checked and all data collected at screening visits 1 and 2 have been keyed to the trial database. Since these processes take time, randomization cannot be done at screening visit 2, and since study medication needs to be issued to the patient, the randomization visit must be completed in person with the patient. Therefore a visit separate from screening visit 2 is necessary. Since this will be a visit on a different calendar day and medication will be started at this visit, good clinical practice requires that a few basic checks of the patient's well-being be completed at the randomization visit.

5. Trial protocol

The procedures completed at the randomization visit are: pregnancy test for women of child bearing potential, verification that the patient is feeling well, affirmation of consent, and generation of the random treatment assignment. The generation process includes the same electronic check on eligibility that the staff may run prior to the randomization visit. The medication assignment will not be generated unless the check finds that the patient is eligible, and the clinic staff indicate that they want to randomize the patient.

The random treatment assignment will consist of medication bottle numbers; these numbers will be unique and will be specific to the particular patient and visit it was generated for. They will correspond to numbered bottles of medications which have been sent to the clinical center's research pharmacy (or clinical coordinator if not using a pharmacy) by the NASH CRN Drug Distribution Center. The research pharmacy (or clinical coordinator) will issue the specific numbered bottles to the patient. Each patient's random treatment assignment will be generated for that specific patient and will not be transferable to another patient. Once the assignment has been generated, the patient should be issued the assigned study drugs (in person) and instructed about starting the drugs and monitoring for adverse effects.

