- Change in insulin resistance (assessed by HOMA), serum vitamin E levels, cytokines, fibrosis markers, and lipid profile after 96 weeks of treatment compared to baseline.
- Change in health-related quality of life (SF-36) after 96 weeks of treatment compared to baseline.

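### Baseline weight, waist, skin fold and lipids date from screening visit 1 (lipids possibly from the chart), so change over 96 weeks of treatment includes pre-treatment change

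*Protocol*

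**What the plan says.** **Anthropometry.** Section 5.2 places the body measurements at S1, in a list that opens "Anthropomorphic assessments (body weight [kg], body height [m], body mass index [BMI], waist circumference [cm" and goes on to hip, waist-to-hip ratio, triceps skin fold and mid-upper arm circumference. Appendix 9.3 marks the detailed physical examination at S1 and marks no examination at screening visit 2 (S2) or at randomization.

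**Lipids.** The S1 laboratory list begins "Laboratory test results that need to be recorded from chart review or obtained as part of screening visit 1 include" and ends with "fasting lipid profile (total cholesterol, triglyceride, LDL, HDL). Frequency and amount of alcohol intake will be obtained". The same paragraph explains that "Determination of eligibility will be based mostly on chart review of standard of care tests and procedures that were completed before screening visit 1". No maximum age is given for a chart lipid result. Appendix 9.3 marks lipids at S1 and then not until week 48.

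**Timing.** Section 5.1 gives "Screening for eligibility for enrollment (2 visits over a maximum of 24 weeks", Section 3.1 also gives 24 weeks, and the synopsis gives 6 months. For the day of the first dose, Section 5.3 says "The procedures completed at the randomization visit are: pregnancy test for women of child bearing potential, verification that the patient is feeling well", followed by affirmation of consent and the assignment. No weight, waist or blood draw for lipids is listed. Study drug starts at that visit, and all follow-up visits, including week 96, are counted from that date.

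**Outcomes.** Section 6.2 lists change in weight, BMI, waist-to-hip ratio, waist circumference, skin fold and total body fat, and separately "lipid profile after 96 weeks of treatment compared to baseline". It names no baseline later than screening.

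**The concern.** A change score attributed to 96 weeks of treatment should start close to the first dose. Here it starts at S1, and the protocol itself schedules influences on these measures between S1 and dosing. At S2, "All patients will be given information on a healthy life style and diet". During screening, patients are asked to stop agents such as metformin and gemfibrozil, and the synopsis allows for at least 3 months of washout. A lipid panel from S1 or the chart could thus reflect a drug that the patient no longer takes at week 96. It could also predate the 3 months of stable statin or fibrate dose that exclusion 10 requires.

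The choice also departs from the protocol's own division of labour. Section 5.2 makes S1 the eligibility visit and S2 the visit that completes baseline data. Aminotransferases, OGTT with insulin, DEXA and SF-36 follow that plan; weight, waist and lipids do not. Within one outcome item, total body fat has an S2 baseline while weight, waist and skin fold have an S1 baseline.

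Weight deserves care because Section 3.3.2 names weight gain as an adverse effect of the drug class, citing 3.2 kg over one year in a pioglitazone pilot study.

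**Working it through.** **1. The plan's own figure.** The only related figure is the sample size in Section 6.5. With placebo 0.14, active 0.40, mean 0.27, two-sided alpha 0.025 and power 90%: n = [2.2414 × √(2 × 0.27 × 0.73) + 1.2816 × √(0.14 × 0.86 + 0.40 × 0.60)]² / 0.26² = 70.1, so 71 per group. Then 71 / 0.9 = 78.9, stated as about 80. It reproduces. It concerns biopsies and is not in dispute; it supplies 80 × 0.9 = 72 evaluable patients per group for step 5.

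**2. Length of the measured interval.** Interval = gap + 96 weeks; pre-treatment share = gap / interval.

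| S1-to-randomization gap | Interval | Pre-treatment share |
|---|---|---|
| 4 weeks | 100 | 4.0% |
| 12 weeks | 108 | 11.1% |
| 24 weeks (Sections 3.1, 5.1) | 120 | 20.0% |
| 26.1 weeks (synopsis, taking 6 months as 183 days) | 122.1 | 21.4% |

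This 120-week interval is not the protocol's week-120 visit. For chart lipids the protocol states no bound.

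**3. Effect on means.** A mean pre-dose change of m shifts every arm's mean change by m. S1 precedes randomization, so m cancels in expectation between arms but stays in each within-arm change.

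**4. Effect on variance.** The documents give no SDs. Assume a 96-week weight-change SD of 6 kg (variance 36) and independent pre-dose drift with SD s. Relative increase = s²/36; equivalent loss of patients = 1 − 36/(36 + s²).

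| Drift SD | Variance increase | Equivalent loss |
|---|---|---|
| 1 kg | 1/36 = 2.8% | 2.7% |
| 2 kg | 4/36 = 11.1% | 10.0% |
| 3 kg | 9/36 = 25.0% | 20.0% |

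If drift variance grows in proportion to time, the increase equals gap/96: 25% at 24 weeks, 12.5% at 12 weeks and about 4% at 4 weeks.

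**5. Illustrative power.** Take a 2.8 kg true difference (the top of the range from placebo-controlled trials cited in Section 3.3.2), two-sided alpha 0.05 and a normal approximation for two means: power = Φ(2.8 / [√(36 + s²) × √(2/72)] − 1.96).

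- s = 0: Φ(2.800 − 1.960) = 80.0%
- s = 1: Φ(2.762 − 1.960) = 78.9%
- s = 2: Φ(2.656 − 1.960) = 75.7%
- s = 3: Φ(2.504 − 1.960) = 70.7%

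Section 6.3 plans Wilcoxon tests for numerical changes, so these values indicate scale only.

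**The case against.** The strongest reply is that nothing here is an error. Section 6.3 compares changes between randomized groups, and S1 values precede randomization, so those comparisons are valid. A reader might infer that the arm comparisons are biased; the documents do not support that. Nor do they support any effect on the primary outcome, aminotransferases, HOMA, DEXA body fat or SF-36, none of which uses an S1 measurement of weight, waist or lipids.

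A reader might also infer that chart lipids of any age will be used. The protocol is silent on age, but Appendix 9.4 budgets a 5 mL fasting lipid draw at S1, so chart use is permitted rather than required, and forms not shown may set a limit. Likewise, a gap beyond 24 weeks for weight and waist has support only in the synopsis wording. Twenty-four weeks is a ceiling: the 183-day biopsy window shortens screening for some patients, and no typical gap is stated.

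Two further points carry weight. The baseline biopsy may itself be 183 days old at randomization, so a screening-period baseline is the trial's general convention. Section 6.1 plans to relate histologic improvement to waist measures, and a later waist baseline could lie further from the biopsy. Also, the document history records that height and weight were removed from the randomization visit in 2005, so their absence was a decision.

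All of this limits the consequence and belongs in the trade-off. It does not remove the point: the log gives no reason for the removal, the S1 values would remain for biopsy-aligned analyses, and no analysis can recover a pre-dose value that was never taken. The week 4 weight, the first after randomization, is already on treatment.

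**Conclusion.** The point holds as a modest design weakness in secondary outcomes. Weight, BMI, waist, waist-to-hip ratio, skin fold and lipids (and upper arm circumference, listed in the synopsis) carry a baseline that can precede treatment by up to 24 weeks, or 6 months under the synopsis, with no stated bound for chart lipids. Change labelled as 96 weeks of treatment can span about 120 weeks. The certain consequence is that within-arm changes are mislabelled. The likely one is lost precision: a 3 to 25% larger variance of weight change, if the 96-week SD is 6 kg and drift is independent with SD 1 to 3 kg. Both SDs are assumptions. Short gaps, or weight lost before dosing and regained later, would make the loss smaller. Between-arm estimates remain unbiased, and the sample size is unaffected.

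**What to change.** - In Section 5.3 and Appendix 9.3, add weight, waist, hip and triceps skin fold at the randomization visit, before the first dose. Name these values in Section 6.2 as the outcome baseline; BMI and waist-to-hip ratio follow from them, with height from S1. Upper arm circumference can be taken at the same time.
- Draw the outcome-baseline lipid profile at S2, which Appendix 9.3 already lists as a fasting visit. Use chart or S1 lipids for screening only.
- Keep the S1 anthropometry for analyses that relate it to the baseline biopsy.

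**Cost.** An amendment, a few minutes at an in-person visit that already takes place, and 5 mL of blood moved from S1 to S2 (the Appendix 9.4 total stays at 605 mL if the S1 lipid draw is dropped). The new anthropometric baseline may lie further in time from the biopsy. Moving lipids to S2 shortens the pre-dose gap without removing it, because no maximum time from S2 to randomization is stated.
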